3.1.1 Dose-Escalation Stage

Cohorts of 3–6 pediatric patients each will be treated at escalating doses of cobimetinib in accordance with the dose-escalation rules described below. The first patient at each dose level must complete at least 5 days of treatment (Days 1–5 of Cycle 1) without a DLT (as defined in Section 3.1.1.1) before subsequent patients can be treated at the same dose level.

The DLT assessment window is defined as Days 1–28 of Cycle 1. Adverse events identified as DLTs, as defined below (see Section 3.1.1.1), will be reported to the Sponsor within 24 hours (see Section 5.4.2).

[figure not shown]
Two formulations will be available for the protocol: a tablet (20 mg) and a suspension (4.8 mg/mL). An MTD or MAD will initially be determined for tablets in patients 6 years and above. Once the MTD or MAD is identified for tablets, enrollment of patients using the suspension will commence following review of relevant data from the tablet dose escalation. The starting dose for the suspension will be a minimum of one dose level below the MTD or MAD of the tablets (see Section 3.1.1.2 for age requirements for suspension). Additional dose escalation with the suspension may proceed according to the dose escalation rules (Section 3.1.1.2) until an MTD or MAD is identified for the suspension. On the basis of an ongoing review of safety data and available PK data, increases in dose level or continued enrollment for either formulation may be halted by the Sponsor as deemed appropriate.

Patients who discontinue from the study prior to completing the DLT assessment window for reasons other than a DLT will be considered non-evaluable for dose-escalation decisions and MTD or MAD assessments. These patients will be replaced at that same dose level unless there are 3 or more patients already treated and all were evaluated with no DLT at that level. Patients who miss five or more doses (i.e., > 18% of the cumulative dose) during the DLT assessment window for reasons other than toxicity will also be replaced. Patients who ingest moderate or strong CYP3A inducers or inhibitors (defined in Appendix 11), ingest prohibited foods/supplements (defined in Section 4.4.3), or receive supportive care during the DLT assessment window that confounds the evaluation of DLTs (not including supportive care described below as part of the DLT definition) may be replaced at the discretion of the Medical Monitor.

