Patients who experience a DLT during the assessment window (first 28 days) may not subsequently continue drug at full dose, even if the drug is withheld until resolution of the toxic event. The investigator should use guidance in Section 5.1.1 and Table 2 (and if guidance is not specified, investigator discretion) to determine whether the patient should permanently discontinue study drug or withhold study drug until toxicity resolves to Grade 1 or lower, then resume study drug at a dose corresponding to a reduction of one dose level.

A study schema for the dose-escalation stage is displayed in Figure 1.

Figure 1 Study Schema: Dose-Escalation Stage

DLT = dose-limiting toxicity.

Note: All patients will receive cobimetinib orally once daily on Days 1–21 of each 28-day cycle. Dose escalation for suspension will proceed in the same way after MTD of tablets has been established, starting at one dose level below the determined MTD or MAD of the tablets, and allowing for enrollment of patients 6 months to 6 years of age as permitted in Section 3.1.1.2.

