3.1.1.1 Definition of Dose-Limiting Toxicity

Any one of the following events will be considered a DLT if it occurs during the DLT assessment window and is assessed by the investigator to be related or possibly related to cobimetinib (rules for attributing causality are defined in Section 5.3.4):

- Grade ≥ 4 neutropenia (ANC $< 0.5 \times 10^9/L$) lasting > 7 days
- Grade ≥ 4 neutropenia with documented infection
- Febrile neutropenia, defined as ANC $< 500/mm^3$ with a single temperature of $> 38.3^\circ C$ ($101^\circ F$) or a sustained temperature of $\geq 38^\circ C$ ($100.4^\circ F$) for more than 1 hour
- Grade ≥ 4 (i.e., life threatening) anemia of any duration

- Grade ≥ 4 thrombocytopenia lasting > 48 hours or any thrombocytopenia requiring a platelet transfusion, with the following exception:
 - For patients who have undergone autologous stem cell transplant or ^{131}I -metaiodobenzylguanidine (MIBG) therapy, Grade ≥ 4 thrombocytopenia lasting > 7 days or any thrombocytopenia requiring a platelet transfusion on two or more separate dates will be considered a DLT.
- Grade ≥ 3 thrombocytopenia with bleeding
- Elevation of serum hepatic transaminase (ALT or AST) $\geq 5 \times$ the upper limit of normal (ULN)
 - For patients with elevated hepatic transaminase levels at baseline as a result of liver metastases, hepatic transaminase $\geq 5 \times$ baseline and $< 10 \times$ baseline for > 3 days, or any hepatic transaminase $\geq 10 \times$ baseline, will be considered a DLT.
- Elevation of serum bilirubin $\geq 3 \times$ ULN
- For patients reliably able to report visual symptoms: Grade ≥ 2 visual disturbance that does not resolve to Grade ≤ 1 within 72 hours after interruption of cobimetinib treatment
- Retinal pathology of any grade, or Grade ≥ 2 uveitis or iritis
- Grade ≥ 2 hemorrhage of any type
- Intracranial hemorrhage of any grade
- Grade ≥ 4 CPK elevation
- Rhabdomyolysis of any grade
 - Rhabdomyolysis includes elevations of CPK in conjunction with either clinical features (such as muscle pain, signs of renal failure, dark red or brown urine) or with laboratory evidence of renal insufficiency (including Grade 2 or higher increased creatinine or creatinine clearance [or radioisotope glomerular filtration rate] < 70 mL/min/1.73 m²), or investigator judgment that a clinical scenario is consistent with rhabdomyolysis.
- Grade ≥ 2 ventricular dysfunction or symptomatic congestive heart failure

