- Reduction in left ventricular ejection fraction (LVEF) below 50% (or shortening fraction below 28%) AND either symptomatic heart failure or a $\geq 10\%$ relative reduction from baseline measurement
 - Note: The relative reduction must be $\geq 10\%$ of baseline function, not an absolute decrease of ≥ 10 percentage points.
- Grade ≥ 4 (i.e., life threatening) vomiting or diarrhea of any duration

- Grade ≥ 3 non-hematologic, non-hepatic, non-ocular adverse event, with the following exceptions, which will not be considered DLTs:
 - Grade ≥ 3 diarrhea or rash that resolves to Grade ≤ 2 within 7 days after interruption of cobimetinib treatment.
 - Grade 3 fever.
 - Grade 3 mucositis or stomatitis that resolves to Grade ≤ 2 within 3 days.
 - Grade ≥ 3 nausea or vomiting that responds to standard-of-care therapy within 3 days.
 - Grade 3 fatigue lasting ≤ 3 days.
 - Grade 3 laboratory abnormalities that are asymptomatic and considered by the investigator not to be clinically significant.

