4.3.2 Dosage, Administration, and Compliance

Cobimetinib will be taken orally once daily on Days 1–21 of each 28-day treatment cycle (21/7 dosing schedule) according to the guidance provided in [Appendix 10](#) until the occurrence of disease progression as determined by the investigator, death, unacceptable toxicity, or patient or investigator decision to discontinue treatment. The starting dose for tablets will be 0.6 mg/kg in the dose-escalation stage. Possible subsequent doses are listed in Section 3.1.1.2. Pediatric patients (< 18 years of age) enrolled in the expansion stage will be treated at or below the MTD or MAD, as determined by the Sponsor. Adult patients (≥ 18 years of age) enrolled in the expansion stage will be treated with the adult recommended dose of 60 mg daily. In case a de-escalation is required in these adult patients, please refer to Section 5.1.1. Patients who reach 18 years of age after starting study therapy will remain on weight-based dosing. Patients will be weighed at the beginning of each cycle. In Cycle 1, weight recorded during the screening period is acceptable. For subsequent cycles, weight must be recorded within 3 days prior to the Day 1 dose, and the dose will be adjusted as needed. No patients will be treated with cobimetinib on Days 22–28 of each cycle.

Patients under 6 years of age or weighing <20 kg are only eligible to receive the drug in suspension (see Section 3.3.1.1 for rationale). Once the suspension is available, the Sponsor will determine whether tablets will remain available to sites based on the observed safety profile and PK of the two formulations, as well as operational feasibility of providing two formulations. If a patient is eligible for treatment with either tablet or suspension formulation, and both formulations are available, the investigator will determine the most appropriate formulation for the patient and enroll the patient into study accordingly. However, patients may not switch formulations after the start of therapy unless safety differences between the two formulations mandate a change for all patients on the study.

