5. ASSESSMENT OF SAFETY

5.1 SAFETY PLAN

The safety plan for patients in this study is based on clinical experience with cobimetinib in completed and ongoing studies. The anticipated important safety risks of cobimetinib are outlined below. Please refer to the cobimetinib Investigator's Brochure for a complete summary of safety information.

Several measures will be taken to ensure the safety of patients participating in this trial. Eligibility criteria have been designed to exclude patients at higher risk for toxicities (see Section 4.1). In addition, patients will undergo safety monitoring during the study as described in Section 4.5, Section 5, and the schedule of assessments (see Appendix 1).

An Internal Monitoring Committee and an Scientific Oversight Committee will monitor patient safety throughout the study. The Internal Monitoring Committee will provide a recommendation on the dose to be taken forward into the expansion stage after completion of the dose-escalation stage (see Section 3.1.3 for details).

Finally, guidelines for managing adverse events, including criteria for dosage modification and treatment interruption or discontinuation, have been provided (see Section 5.1.1). These guidelines apply to patients in the dose-escalation and expansion stages. However, the guidelines are not intended to replace clinical judgment or dictate care of individual patients.

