Decrease in cardiac function has been identified as an adverse event that falls under “Warnings and Precautions” for adult use of cobimetinib. Study GO28141 demonstrated a decrease in cardiac function in 7% of cobimetinib plus vemurafenib-treated patients versus 3% of vemurafenib-treated patients. Most cases were asymptomatic. Symptoms consistently improved following treatment discontinuation, treatment interruption, or dose reduction in the cobimetinib arm, while improvement was inconsistent in the vemurafenib arm. There has been no in vitro or nonclinical evidence of decreased cardiac function with cobimetinib administration.

As there is no biomarker that can accurately identify early decreased cardiac function in children, cardiac function will be assessed through echocardiograms performed at specified timepoints throughout the study (see [Appendix 1](#)). This is particularly important in pediatric patients who have been treated with an anthracycline analogue, and even more so in pediatric patients who have had chest radiotherapy in addition to anthracycline treatment, both of which increase the risk of cardiac dysfunction.

Guidelines for the management of symptomatic reduction in left ventricular ejection fraction are provided in [Table 3](#).

Table 3 Guidelines for Management of Asymptomatic Reduction in Left Ventricular Ejection Fraction

Patient	LVEF Value	Recommended Cobimetinib Dose Modification	LVEF Value Following Treatment Break	Recommended Cobimetinib Daily Dose
Asymptomatic	≥ 50% (or 40%–49% and < 10% absolute decrease from baseline)	Continue at current dose	N/A	N/A
	< 40% (or 40%–49% and ≥ 10% absolute decrease from baseline)	Interrupt treatment for 2 weeks	< 10% absolute decrease from baseline	1 st occurrence: reduce by 1 dose level
				2 nd occurrence: reduce by additional dose level
				3 rd occurrence: permanent discontinuation
< 40% (or ≥ 10% absolute decrease from baseline)			Permanent discontinuation	

LVEF=left ventricular ejection fraction; FS=fractional shortening.

Note: Investigators may substitute FS for LVEF in algorithm above as follows:

- FS ≥ 28% equivalent to LVEF 50%
- FS 25%–27.9% equivalent to LVEF 40%–49%
- FS < 25% equivalent to LVEF < 40%

Patients who require dose reduction should have LVEF measurements at 2, 4, 10, and 16 weeks after diagnosis. Patients with symptomatic heart failure must discontinue study drug.

Rhabdomyolysis and CPK Elevations

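### Table 3 tells investigators to continue full dose after some asymptomatic LVEF falls that Section 3.1.1 treats as dose-limiting and for which it bars full dose

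*Combined protocol and SAP*

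**What the plan says.** Four parts of the combined protocol and SAP bear on this.

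- **DLT definition (Section 3.1.1.1).** An event qualifies only if it falls in the DLT window and "is assessed by the investigator to be related or possibly related to cobimetinib". One listed event is LVEF below 50% (or shortening fraction below 28%) together with either symptomatic heart failure or a 10% or greater "relative reduction from baseline measurement". A note adds that the 10% is a share of baseline function and not percentage points. Symptoms are therefore not required. On the window, Section 3.1.1 states: "The DLT assessment window is defined as Days 1–28 of Cycle 1".
- **Consequence of a DLT (Section 3.1.1).** The patient "may not subsequently continue drug at full dose". The investigator is sent to Section 5.1.1 and Table 2 to decide whether to "permanently discontinue study drug or withhold study drug until toxicity resolves to Grade 1 or lower", in the latter case resuming one dose level lower. Investigator discretion applies only where that guidance is silent.
- **Where the guidance leads.** Section 5.1.1 and the asymptomatic-LVEF entry in Table 2 both refer to Table 3 (Section 5.1.2.1). For LVEF of 50% or more, or 40%–49% with less than a 10% absolute decrease, Table 3 says "Continue at current dose".
- **Scope (Section 5.1).** "These guidelines apply to patients in the dose-escalation and expansion stages". Table 3 makes no exception for a DLT.

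**The concern.** The DLT rule measures the fall relative to baseline, and Table 3 measures it in absolute points. With a baseline near the eligibility floor, a fall can be large enough to be a DLT and still small enough for Table 3 to leave the dose alone. An investigator who follows Section 3.1.1 to the guidance it cites then reaches the one outcome that section forbids.

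At stake is the dose given to an individual child after a cardiac DLT. Section 5.1.2.1 itself stresses cardiac monitoring in patients with prior anthracycline or chest radiotherapy. The DLT count, the escalation decision, the MTD and expansion-stage patients are not affected.

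**Working it through.** **Inputs**

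- Baseline LVEF B is at least 50% where LVEF is measured (Section 4.1.1).
- On-treatment LVEF L lies in 40–49 (Table 3 band; also below the DLT threshold of 50%).
- DLT rule: (B − L)/B ≥ 0.10 (Section 3.1.1.1).
- Table 3 rule for continuing: B − L < 10, reading absolute decrease as percentage points, in line with the contrast drawn in Section 3.1.1.1.

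**Overlap, whole percentages**

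| Baseline B | On-treatment L in conflict | Fall (points) | Pairs |
|---|---|---|---|
| 50 | 41–45 | 5–9 | 5 |
| 51 | 42–45 | 6–9 | 4 |
| 52 | 43–46 | 6–9 | 4 |
| 53 | 44–47 | 6–9 | 4 |
| 54 | 45–48 | 6–9 | 4 |
| 55 | 46–49 | 6–9 | 4 |
| 56 | 47–49 | 7–9 | 3 |
| 57 | 48–49 | 8–9 | 2 |
| 58 | 49 | 9 | 1 |
| ≥ 59 | none | – | 0 |

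Total: 5 + 4 × 5 + 3 + 2 + 1 = 31 pairs. At B ≥ 59, L ≤ 49 makes the fall at least 10 points, and Table 3 then interrupts treatment.

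Example: B = 55, L = 48. Relative fall = 7/55 = 12.7%, so it is a DLT. Absolute fall = 7 points, so Table 3 continues the dose. The largest relative fall in the overlap is 50% to 41%: 9/50 = 18%.

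**When it can be detected**

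The first scheduled on-treatment echocardiogram is at Cycle 2 (Section 4.5.7; Appendix 1). Taking it as tied to Cycle 2 Day 1, as the Appendix 1 column implies, that is study Day 28 + 1 = 29. The ±3-day window gives Days 26–32, of which Days 26, 27 and 28 (3 of 7) lie in the DLT window. Section 4.3.2 states: "No patients will be treated with cobimetinib on Days 22–28 of each cycle". For the scheduled scan, then, the only decision at stake is the Cycle 2 dose. An unscheduled scan on Days 1–21 could also put the remaining Cycle 1 doses at issue.

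**Comparison with other DLT events in Table 2**

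Grade 2 hemorrhage, ALT or AST at or above 5 × ULN, serous retinopathy and Grade 4 CPK elevation all first stop the drug. Section 3.1.1 can then supply the reduced dose. The Table 3 row is different because it never stops the drug.

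**Fractional shortening**

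The Table 3 note maps FS 25%–27.9% to LVEF 40%–49% but gives no absolute FS limit. If the 10-point limit were applied to FS (an assumption), 32% to 26% would be a 6-point fall and 6/32 = 18.8% relative, which is the same conflict. The conclusion does not rest on this.

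**The case against.** The best reply is that Section 3.1.1 already settles the matter. It is the specific rule for DLTs and is worded as a prohibition, whereas the Table 3 column is headed as a recommendation and Section 5.1 adds that the guidelines do not replace clinical judgment. Section 3.1.1 sends the reader to the guidance only to choose between stopping and withholding. Since Table 3 offers neither, the guidance could be called silent, leaving the investigator discretion between those two. Table 2 has no DLT exceptions either: after recovery from a visual disorder it states no reduction, and after Grade 4 CPK elevation it reduces only where clinically indicated. Finally, DLTs reach the Sponsor within 24 hours, so an error might be caught.

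Much of this stands. Section 3.1.1 is the firmer text and should prevail, and prompt reporting makes an unnoticed error less likely. But no sentence states the precedence. Nor is the guidance silent: it names this event and gives an instruction. The Table 2 rows cited differ in kind, because they stop the drug before the question of dose arises.

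**Conclusion.** The conflict is real but minor. It is confined to dose-escalation patients with an asymptomatic, drug-related fall in Days 1–28, a baseline LVEF of 50%–58% and a fall of 5–9 points in whole percentages. There is no conflict in the expansion stage, after Day 28, for events judged unrelated, or when the fall is 10 points or more or LVEF is below 40%.

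The documents give no LVEF distribution, so no frequency can be stated; given the scan schedule the case should be uncommon. The conclusion assumes that absolute decrease means percentage points. The 3-of-7-days figure further assumes that the Cycle 2 echocardiogram is timed from Cycle 2 Day 1.

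**What to change.** Add one sentence to Table 3, for example:

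> In the dose-escalation stage, the row reading "Continue at current dose" does not apply to an event that meets the LVEF/FS criterion of Section 3.1.1.1 within the DLT assessment window; Section 3.1.1 governs, and the drug is either discontinued or withheld and resumed one dose level lower.

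Both thresholds stay as they are. Nothing in the design, DLT counting or analysis changes, so the cost is a single line in the next amendment. The same amendment can correct a clerical slip: the sentence introducing Table 3 refers to symptomatic reductions, while the table title says asymptomatic.

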Female patients must remain abstinent or use single or combined contraceptive methods that result in a failure rate of $< 1\%$ per year during the treatment period and for at least 3 months after the last dose of study drug. Female patients must refrain from donating eggs during this same period.

True abstinence is only acceptable if it is in line with the preferred and usual lifestyle of the patient. Periodic abstinence (e.g., calendar, ovulation, symptothermal, or postovulation methods) and withdrawal are not acceptable methods of contraception.

Examples of contraceptive methods with a failure rate of $< 1\%$ per year include, hormonal implants, established, proper use of combined oral or injected hormonal contraceptives, and certain intrauterine devices. Alternatively, two methods (e.g., two barrier methods such as a condom and a cervical cap) may be combined to achieve a failure rate of $< 1\%$ per year. Barrier methods must always be supplemented with the use of a spermicide.

- For male patients with a female partner of childbearing potential or a pregnant female partner: Agreement to remain abstinent or use a condom during the treatment period and for at least 3 months after the last dose of study drug
 - True abstinence is only acceptable if it is in line with the preferred and usual lifestyle of the patient. Periodic abstinence (e.g., calendar, ovulation, symptothermal, or postovulation methods) and withdrawal are not acceptable methods of contraception.
- For male patients: agreement to refrain from donating sperm during the treatment period and for at least 3 months after the last dose of study drug
- Adequate hematologic and end organ function, defined by the following laboratory results obtained within 28 days prior to initiation of study drug:
 - ANC $\geq 0.75 \times 10^9/L$ (unsupported)
 - Platelet count $\geq 75 \times 10^9/L$ (unsupported)
 - Hemoglobin ≥ 8 g/dL (transfusion is acceptable to meet this criterion)
 - Bilirubin $\leq 1.5 \times ULN$ for age
 - AST and ALT $\leq 2.5 \times ULN$ for age
 - Serum creatinine $\leq 1.5 \times ULN$ for age or creatinine clearance (or radioisotope glomerular filtration rate) > 70 mL/min/1.73 m²
- Fractional shortening (FS) $\geq 30\%$ and LVEF $\geq 50\%$ at baseline, as determined by echocardiography or multigated acquisition scan (MUGA) within 28 days prior to initiation of study drug

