 - Depending on institutional standard, either FS or LVEF is adequate for enrollment if only one value is measured; if both values are measured, then both values must meet criteria above.
- Body weight must be ≥ 20 kg if suspension is not available

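### Table 3 converts LVEF levels to fractional shortening but not the 10-point fall, so some eligible children meet both the dose-reduction and the permanent-discontinuation row after a treatment break

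*Combined protocol and SAP*

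**What the plan says.** Section 5.1.1 directs that asymptomatic LVEF declines be managed by the algorithm in Table 3, which has two steps.

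- **On treatment.** Dosing continues if LVEF is "≥ 50% (or 40%–49% and < 10% absolute decrease from baseline". It is interrupted for 2 weeks if LVEF is "< 40% (or 40%–49% and ≥ 10% absolute decrease from baseline".
- **After the break.** If the value shows "< 10% absolute decrease from baseline", the dose is lowered at the first and second occurrence and treatment ends at the third. If the value is "< 40% (or ≥ 10% absolute decrease from baseline", treatment ends permanently. The first of these rows sets no level. No order of precedence is given.

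The note to Table 3 adds: "Investigators may substitute FS for LVEF in algorithm above as follows". It pairs FS of 28% or more with LVEF 50%, and FS 25%–27.9% with LVEF 40%–49%. For the lowest level it reads "FS < 25% equivalent to LVEF < 40" per cent. It says nothing about the 10-point fall.

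The inclusion criteria (section 4.1.1) set baseline floors of 30% for FS and 50% for LVEF, with no upper limit on either. They add that "either FS or LVEF is adequate for enrollment if only one value is measured".

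**The concern.** A rule that mixes a level with a change has to be converted in both parts when the measurement scale changes. Table 3 converts only the level. On LVEF, the eligibility floor of 50% lies 10 points above the 40% cut. That gap, which equals the change criterion, is what keeps the two post-break rows apart. On FS, the floor of 30% lies only 5 points above the 25% cut, so the rows can overlap.

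At stake is whether a child whose FS has not recovered goes back on a lower dose or stops for good. Both outcomes weigh heavily. Eligibility is limited to disease with no known curative therapy, and section 5.1.1 bars re-escalation. Section 5.1.2.1 also stresses cardiac monitoring for children previously given anthracyclines or chest radiotherapy. Two sites could follow the same table and treat identical children differently.

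**Working it through.** The plan states no figure to reproduce. This is a check of logic.

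**Inputs.** Let b be baseline and x the later value, both in percentage points.
- LVEF: b ≥ 50 (section 4.1.1); cuts at 40 and 50 (Table 3).
- FS: b ≥ 30 (section 4.1.1); cuts at 25 and 28 (Table 3 note).
- Change criterion: b − x compared with 10, as printed, on either scale.

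**Step 1. Post-break rows on LVEF.** Both rows apply if x < 40 and b − x < 10. With b ≥ 50 and x < 40, b − x is always more than 10. There is no overlap. Enumerating baselines from 50% to 75% in steps of 0.1 also found none.

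**Step 2. Post-break rows on FS.** Both rows apply if x < 25 and b − x < 10, that is, if b − 10 < x < 25. This interval is non-empty when b < 35. With the eligibility floor, the affected baselines run from 30% to below 35%.

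| Baseline FS (%) | Post-break FS meeting both rows, one decimal | Whole numbers |
|---|---|---|
| 30 | 20.1–24.9 | 21–24 |
| 32 | 22.1–24.9 | 23–24 |
| 33 | 23.1–24.9 | 24 |
| 34 | 24.1–24.9 | none |
| 35 | none | none |

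Recorded to one decimal, the last affected baseline is 34.8%. In whole numbers it is 33%.

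**Step 3. The situation is reachable.** Take baseline FS 32% and an on-treatment value of 24%. Since 24 < 25, treatment is interrupted. Suppose FS is still 24% after 2 weeks. The fall is 32 − 24 = 8, which is below 10, so the dose-reduction row applies. FS is also below 25%, so the permanent-discontinuation row applies. At the third occurrence both rows end treatment, so the conflict concerns the first two.

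**Step 4. The middle band (secondary).** Interruption within FS 25%–27.9% needs b − x ≥ 10 with x ≥ 25, so b ≥ 35. For b < 35 the largest fall in the band is b − 25, which is below 10. The change criterion therefore has no effect there and dosing continues throughout the band. From b = 35 it does act: at FS 25.0% for baseline 35.0%, at 25.0%–26.0% for baseline 36.0%, and across the whole band from baseline 37.9%. On LVEF, baseline 50% triggers in the 40%–49% band only at exactly 40%.

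**The case against.** The best reply on the main point is that the discontinuation row is an either-or rule in which the level alone suffices, and that the dose-reduction row is naturally read as the recovered case. That reading is sensible, but Table 3 does not state it. As printed, a child with no recovery at all can satisfy the dose-reduction row.

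The change could also be meant in LVEF-equivalent units, which would remove the overlap. The table does not say so, and level bands do not allow such a change to be calculated.

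Other safeguards exist. Section 5.1 says the guidelines do not replace clinical judgment. Substitution is optional. LVEF is to be measured at 2, 4, 10 and 16 weeks in patients who need dose reduction, and week 2 may coincide with the end of the break. An LVEF reduction of Grade 2 or higher is reportable within 24 hours (section 5.2.3). These lessen the risk but do not say which row governs. A child enrolled on FS alone may also have no baseline LVEF from which to measure a fall.

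Four stronger readings are tempting, and the documents do not support them.
- A reader might infer that the FS middle band can never trigger an interruption. That holds only for baseline FS below 35%. FS below 25% still interrupts by level at any baseline, and the contrast with LVEF is one of degree.
- A reader might infer from the band widths that 3 FS points equal 10 LVEF points. No conversion of change is given. Eligibility also sets FS 30% beside LVEF 50%, while Table 3 pairs FS 28% with LVEF 50%. The overlap does not depend on any such ratio.
- A reader might infer that follow-up on FS alone is expressly approved. Section 4.1.1 speaks of enrolment only.
- A reader might infer that FS substitution should be withdrawn. That is a clinical choice for the sponsor, and it could require LVEF where only FS is now measured.

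**Conclusion.** The inconsistency is real and limited. Under direct substitution, a child with baseline FS from 30% to below 35%, and post-break FS below 25% but less than 10 points under baseline, meets two incompatible rows at the first or second occurrence. For an eligible LVEF baseline this cannot happen. The secondary point is that the change criterion does nothing in the 25%–27.9% band for those same baselines.

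The conclusion assumes that the 10 points are read on the FS scale as printed and that no unstated precedence applies. The documents give neither a baseline FS distribution nor a count of children followed on FS, so the frequency is unknown. No efficacy endpoint or analysis is affected, and the cardiac dose-limiting toxicity rule in section 3.1.1.1, which uses a relative fall, is a separate matter. The reason to act is safety and consistent handling across sites.

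**What to change.** The sponsor's clinicians should reconcile three elements in the Table 3 note: the FS level equivalents, the change criterion when FS is used, and the relation between the two post-break rows. The test of success is that exactly one row applies, at each step, for any eligible FS baseline and any later FS value. The algebra above can be rerun on the revised wording to confirm it. Which values or which row should govern is theirs to decide.

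The cost is a short edit to a table note at the next amendment, plus the clinical discussion behind it. No new assessment is needed if the reconciliation stays within measurements already taken.
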